**Statistical Analysis Plan**

Sponsor: Zogenix International Limited; Protocol No.: ZX008 Study 2 (ZX008-1501 and ZX008-1502)

Listing	16.2.6.8	Parent/Caregiver Ratings using HADS Scale
Listing	16.2.6.9.1	Pediatric Quality of Life Inventory (Peds QL) - for TODDLERS (age 2-4 years)
Listing	16.2.6.9.2	Pediatric Quality of Life Inventory (Peds QL) - for Young Children (age 5-7 years)
Listing	16.2.6.9.3	Pediatric Quality of Life Inventory (Peds QL) - for Children (age 8-12 years)
Listing	16.2.6.9.4	Pediatric Quality of Life Inventory (Peds QL) - for TEENS (age 13-18 years)
Listing	16.2.6.9.5	Pediatric Quality of Life Inventory (Peds QL) – Family Impact Module
	16.2.7	Adverse events
Listing	16.2.7.1	Adverse Events
Listing	16.2.7.2	Adverse Events Of Special Interests (AESI)
	16.2.8	Laboratory data
Listing	16.2.8.1.1	Laboratory Data Hematology Parameters
Listing	16.2.8.1.2	Extreme Value Laboratory Parameters - Hematology
Listing	16.2.8.2.1	Laboratory Data Biochemistry Parameters
Listing	16.2.8.2.2	Extreme Value Laboratory Parameters - Biochemistry
Listing	16.2.8.3.1	Laboratory Data Coagulation Parameters
Listing	16.2.8.3.2	Extreme Value Laboratory Parameters - Coagulation
Listing	16.2.8.4.1	Laboratory Data Urinalysis Parameters
Listing	16.2.8.4.2	Extreme Value Urinalysis Data
Listing	16.2.8.5	Tests of Growth and Precocious Puberty
Listing	16.2.8.6	Urine Pregnancy Test
Listing	16.2.8.7	Urine THC Panel
Listing	16.2.8.8	Whole Blood Cannabidiol
	16.2.9	Other Safety Data
Listing	16.2.9.1.1	Vital Signs
Listing	16.2.9.1.2	Abnormal Vital Signs Data
Listing	16.2.9.2	Columbia-Suicide Severity Rating Scale (C-SSRS)
Listing	16.2.9.3.1	Behavior Rating Inventory of Executive Function – Preschool Version (BRIEF-P)
Listing	16.2.9.3.2	Behavior Rating Inventory of Executive Function (BRIEF)
Listing	16.2.9.4	Tanner Staging
Listing	16.2.9.5	Physical Examination
Listing	16.2.9.6	Neurological Examination
Listing	16.2.9.7	Epilepsy Genotype Panel

This document is confidential.

## Abbreviations and Definitions of Terms

ΔΔQTcF	Change from baseline and placebo (Double-Delta) in QTcF
ACI	Abnormal Clinically Insignificant
ANOVA	Analysis of Variance
APCS	Abnormal Potentially Clinically Significant
bpm	Beats per minute
Cmax	Maximum Plasma Concentration
CI	Confidence Interval
CL/F	Oral dose apparent clearance
DS	Dravet's Syndrome
ECG	Electrocardiogram
Emax	Maximum Effect
GSMB	Global Superimposed Median Beat
kg	Kilogram
h, hr	Hour
HR	Heart Rate
m	Minutes
mg	Milligram
mL	Milliliter
mm	Millimeter(s)
mmHg	Millimeters of Mercury
ms	Millisecond(s)
N	Sample Size
ng	Nanogram
PAH	Pulmonary Arterial Hypertension
PD	Pharmacodynamic
PK	Pharmacokinetic
PP	Per Protocol
PR	Interval between the start of the P wave and start of the Q wave
QRS	QRS waves complex on the electrocardiogram tracing
QT	Interval between the start of the Q wave and the end of the T wave
QTc	Corrected QT duration
QTcF	QT interval corrected using Fridericia's formula
RR	The time interval between consecutive heart beats.
SAP	Statistical Analysis Plan
SD	Standard Deviation

Statistical Analysis Plan

Status: Final Version 1.0

Revised: 09Jun2020

Protocol #: ZX008-1501, ZX008-1502; "Study 2"

Page 6 of 23

s	Second(s)
SMEI	Severe Monoclonal Epilepsy of Infancy
SUPED	Sudden Infant Death in Epilepsy
tmax	Time to maximum concentration (C max )
t1/2	Half-life associated with terminal phase of the concentration-time profile
TdP	Torsade de Pointes
ZX008	Fenfluramine Hydrochloride

PUBLIC COPY

This document cannot be used to support any marketing authorization application and any extensions or variations thereof.

Statistical Analysis Plan	
Status: Final Version 1.0	Revised: 09Jun2020

## 1. Introduction

ZX008 (fenfluramine hydrochloride) is under clinical development for the adjunctive treatment of patients with Dravet syndrome (DS). DS, also known as severe myoclonic epilepsy of infancy (SMEI), is a rare and severe form of epilepsy first described by Charlotte Dravet in 1978 (Dravet 1978). The condition most commonly appears during the first year of life as frequent febrile seizures. As the condition progresses, other types of seizures typically occur, including myoclonic seizures and status epilepticus (Dravet 1978). Following the appearance of these seizures, affected children develop several co-morbid conditions including psychomotor regression, ataxia, sleep disturbance, and cognitive impairment. Cognitive impairment begins to become apparent around age 2 years due to lack of intellectual/behavioral progression. Dravet children often have a lack of coordination, poor development of language, hyperactivity, and difficulty relating to others (Dravet 1978; Hurst 1990). The degree of cognitive impairment appears to correlate, at least in part, with the frequency of seizures, and might be a result of repeated cerebral hypoxia. Children with DS also encounter a higher incidence of Sudden Unexpected Death in Epilepsy (SUDEP; Nashef 2012) than other populations with epilepsy. Indirect evidence has linked SUDEP to several possible etiologies, including seizure-induced apnea, pulmonary edema, dysregulation of cerebral circulation, and cardiac arrhythmias (Shorvon 2011), although the actual etiology remains unknown and other mechanisms have not been ruled out. The vast majority of patients who survive to adulthood are wholly dependent on around-the-clock caregivers and usually live in institutional care homes.

The primary known pharmacologic action of fenfluramine is serotonin release in the CNS (Baumann, 2014); preliminary evidence suggests a role for other mechanisms of action as well. Fenfluramine is readily absorbed after oral administration with an oral bioavailability of 60-70% (Bever and Perry, 1997) and a Tmax of 4 hours (Beckett & Brookes, 1967). Terminal half-life (t1/2) is approximately 20 hours for the parent and 30 hours for the active metabolite, norfenfluramine. Metabolism occurs primarily by Cytochrome P450 (CYP)1A2, CYP2B6 and CYP2D6. CYP2C9, CYP2C19 and CYP3A4 also appear to be involved, but to a lesser degree. Elimination of the drug and its metabolites is largely renal. The drug readily crosses the blood brain barrier and is widely distributed in all tissues.

When fenfluramine was marketed for treatment of obesity at doses of 60-120 mg/day, reports of cardiac valvular disease emerged (Connolly, 1997). The FDA issued an advisory request for information from similar cases and eventually requested voluntary withdrawal of fenfluramine and dexfenfluramine from the market in 1997. There were 144 individuals reported to have valvulopathy involving fenfluramine or dexfenfluramine in the initial 1997 communication (CDC, 1997). Of 113 confirmed cases, 111 occurred among women; the median age was 44 years (range: 22-68 years). Of these 113 cases, 2 (2%) used fenfluramine alone; 16 (14%) dexfenfluramine alone; 89 (79%) a combination of fenfluramine and phentermine; and 6 (5%) a combination of all 3 drugs. The median duration of drug use was 9 months (range: 1-39 months). Overall, 87 (77%) of the 113 cases were symptomatic and 24 (27%) required valve replacements.

The prevalence of valve lesions was assessed for patients who were exposed to these drugs but who had no obvious history of cardiac disease or cardiac symptoms in 5 independent unpublished echocardiographic surveys submitted to FDA in 1997. These surveys demonstrated a prevalence of valvular disease meeting the case definition ranging from 30.0% to 38.3% (overall: 32.8%; 95% confidence interval=27.7%-38.9%). However, subsequent studies sought to estimate the risk of valvulopathy in fenfluramine-treated adult obese patients and found fenfluramine-associated valvular disease was less common than the original observational reports suggested, approximately 9.6% for aortic valve dysfunction (range 5.0% to 26.3%) and 3.1% for mitral regurgitation of mild severity or greater (Loke, 2002; Sachdev, 2002).

In 1981, a report was published describing 2 patients who developed pulmonary hypertension while taking fenfluramine (Douglas, 1981). Additional rare cases, some of which were severe or even fatal, were reported subsequently (McMurray, 1986; Pouwels, 1990).

Zogenix has evaluated the effect of multiple oral administrations of therapeutic (30 mg/day, ie, 15 mg BID) and suprathreshold (120 mg/day, ie, 60 mg BID) doses of ZX008 on the heart rate corrected QT interval using Fridericia's formula (QTcF) in healthy adult volunteers (Study 1603). The suprathreshold ZX008 dose of 120 mg/day provided a 4-fold higher dose than the maximum dose planned for clinical use, while maintaining a reasonable safety margin. This study demonstrated that there is no significant effect of ZX008 on QTc intervals at either the therapeutic or suprathreshold dose; multiple therapeutic and suprathreshold doses of ZX008 do

Statistical Analysis Plan	
Status: Final Version 1.0	Revised: 09Jun2020

not prolong QTcF intervals. Following multiple doses of 15 mg and 60 mg ZX008, trough levels of fenfluramine and norfenfluramine indicated that steady state was effectively reached prior to the end of the 7-day interval. Zogenix has reported safety and efficacy data from 2 adequate and well controlled studies, Study 1 and Study 1504 Cohort 2, and 1 interim analysis from the open-label extension study (Study 1503). Study 1 represents the first 119 subjects randomized in two identical and parallel studies, 1501 and 1502, and compared 2 doses of ZX008, 0.2 mg/kg/day and 0.8 mg/kg/day (up to a maximum of 30 mg/day), to placebo in subjects receiving standard of care anti-epileptic treatments excluding stiripentol (STP). Study 1504 Cohort 2 compared a dose of ZX008 0.5 mg/kg/day (up to a maximum of 20 mg/day) to placebo in subjects receiving standard of care anti-epileptic treatments where administration of STP (in combination with clobazam [CLB] and/or valproate [VPA]; i.e., the STP regimen) was mandatory. A prospectively-defined cardiovascular monitoring program that employed color Doppler echocardiography (ECHO) and electrocardiograms was implemented in the ZX008 clinical program (all Dravet syndrome trials) to monitor for valvular heart disease (VHD) or pulmonary artery hypertension (PAH); this ECHO program was designed with input from FDA and from cardiology experts. As of the writing of this Statistical Analysis Plan, no study subject in the entire ZX008 program, has developed VHD or PAH.

This Statistical Analysis Plan (SAP) for Cardiovascular Endpoints outlines the planned analyses to support the assessment of electrocardiographic (ECG) and echocardiographic data in the Study 2 clinical study report. Study 2 represents all subjects enrolled in Study 1501 and 1502 who were not included in Study 1. The planned analyses identified in this SAP may be included in regulatory submissions, and exploratory analyses not defined in this SAP may be performed to support a more thorough understanding of the safety data. All post-hoc or unplanned analyses performed not identified in this SAP will be documented.

Documents used to develop this SAP are:

- Study Protocol ZX008-1501 (Amendment 3.0, 31-October-2016).
- Study Protocol ZX008-1502 (Amendment 2.4.3, 07-February-2019).
- Study 1 Statistical Analysis Plan (Version 2.1, 17-September-2017).
- CAMI 7 12-Lead Analysis Plan for use with Eli 150c (Inventive Health/Zogenix) (Version 1.0, 11-January-2016).
- ZX008 Investigational Brochure (Version 7, 31-July-2019).

## 2. Study Design and Cardiovascular Analysis Objectives

### 2.1 General Design and Plan

Study 2 contains pooled data from two studies, 1501 and 1502. Both studies are multicenter, randomized, double-blind, parallel group, placebo-controlled trials of two fixed doses of ZX008 (Fenfluramine Hydrochloride) oral solution as adjunctive therapy in children and young adults with Dravet syndrome. The first 119 subjects randomized were reported as Study 1; Study 2 represents all subjects enrolled in Study 1501 and 1502 who were not included in Study 1.

Each subject is assigned to one of 2 treatments (0.2 mg/kg or 0.8 mg/kg) or placebo. Treatments were assigned on a 1:1:1 basis.

Electrocardiograms (ECGs) and echocardiograms (ECHOs) are being analyzed by ERT (formerly Biomedical Systems (St. Louis, MO)).

All ECGs were reviewed and interpreted by a board-certified cardiologist. Echocardiograms were reviewed by two, board-certified cardiologists. In the case of a discrepancy between the readers, the echocardiogram was sent to adjudicators for final reading. At the initiation of the ZX008 Program, the International (Pediatric) Cardiology Advisory Board (ICAB) was set-up to oversee the vendor's ECHO readings. ICAB members were chosen solely based on their academic credentials and experience, with the Chair being chosen based upon his/her seniority and respect in the field of echocardiography. When there was a differing interpretation of findings in an ECHO of any subject between the vendor and ICAB (either in the alert level of valvular regurgitation or presence or absence of pulmonary hypertension), the following process occurred: a telephone conference call was to be held with the vendor ERT cardiology readers and ICAB reader and ICAB Chair (if the

Statistical Analysis Plan	
Status: Final Version 1.0	Revised: 09Jun2020

Chair was reader, then only he/she will be on call) to discuss the ECHO findings and try to come to an agreement on interpretation; if agreement could not be reached then ICAB Chair read the ECHO and his/her reading become the official reading. This one ECHO report was then be sent to the IDSMC.

## 2.2 Objectives

The primary objective of Study 2 is to demonstrate that ZX008 0.8 mg/kg/day is superior to placebo as adjunctive therapy in the treatment of Dravet syndrome in children and young adults based on change in the frequency of convulsive seizures between baseline and the combined Titration and Maintenance Periods (T+M). Safety endpoints of the study include the assessment for cardiac toxicity as demonstrated by ECG and ECHO.

### 2.2.1. Cardiovascular Safety Objectives

The primary cardiovascular safety objective of this analysis is to evaluate the effect of ZX008 on the heart as demonstrated by both the 12-lead ECG and ECHO.

Variables included in the analysis are listed below. These will be compared between Placebo and the 0.2 mg/kg and 0.8 mg/kg groups independently.

## 2.3 Endpoints

### 2.3.1 ECG

The change from baseline will be calculated and compared between placebo and the two dosing groups (0.2 mg/kg and 0.8 mg/kg) for the main and secondary ECG endpoints for each of the variables and subgroups listed.

#### 2.3.1.1 Main Focus of ECG Analysis

The main focus for ECG will be the mean change between measurements of QT interval corrected using Fridericia's formula (QTcF) for ZX008 and placebo after baseline adjustment, ( $\Delta\Delta\text{QTcF}$ ), calculating the upper bound of the one-sided 95% confidence interval.

#### 2.3.1.2 Other ECG Analyses

Other secondary endpoints that will be presented by dose and subgroups are:

- Mean QTcF duration including changes from baseline ( $\Delta\text{QTcF}$ )
- Mean QRS duration (including changes from baseline ( $\Delta\text{QRS}$ ) and from placebo and baseline ( $\Delta\Delta\text{QRS}$ ))
- Mean PR interval measurements (including changes from baseline ( $\Delta\text{PR}$ ) and from placebo and baseline ( $\Delta\Delta\text{PR}$ ))
- Mean Heart rate (including changes from baseline ( $\Delta\text{HR}$ ) and from placebo and baseline ( $\Delta\Delta\text{HR}$ ))
- Categorical analyses for each variable and subgroup listed below:
  - QTcF (number and percentage of subjects, by dose)

Age	Gender	Values
0 to < 12 years	Males and Females	< 320 ms
		$\geq 320\text{ms to } \leq 450\text{ ms}$
		> 450 ms to $\leq 480\text{ ms}$
		> 480 ms
12 to 18 years	Males	< 320 ms
		$\geq 320\text{ ms to } \leq 450\text{ ms}$
		> 450 ms to 500 ms
		> 500 ms
12 to 18 years	Females	< 320 ms
		$\geq 320\text{ ms to } \leq 470\text{ ms}$
		> 470 ms to $\leq 500\text{ ms}$
		> 500 ms

Statistical Analysis Plan	
Status: Final Version 1.0	Revised: 09Jun2020

- For all ages QTcF changes from baseline (number and percentage of subjects, by dose)
  - ≤ 30 ms
  - > 30 ms to ≤ 60 ms
  - > 60 ms
- QRS (number and percentage of subjects, by dose)

Age	Gender	Values
2 to <6 years	Males and Females	≤ 90 ms
		>90ms to ≤100ms
		> 100 ms
		≤ 100 ms
6 to < 12 years	Males and Females	> 100 ms to ≤ 110 ms
		> 110 ms
		≤110ms
		>110 ms to ≤ 120ms
12 to 18 years	Males and Females	>120ms
		≤ 90 ms

- PR (number and percentage of subjects, by dose)

Age	Gender	Values
2 to <6 years	Males and Females	≤ 90 ms
		> 90ms to ≤ 150 ms
		>150 ms
6 to < 12 years	Males and Females	≤ 100 ms
		> 100 ms to ≤ 170 ms
		>170 ms
12 to 17 years	Males and Females	≤110ms
		>110 ms to ≤ 180ms
		>180ms
18 years	Males and Females	≤120 ms
		>120 ms to ≤ 220ms
		>220 ms

- Heart rate (number and percentage of subjects, by dose)

Age	Gender	Values
2 to <6 years	Males and Females	<80 bpm
		≥80 bpm to ≤140bpm
		> 140 bpm to ≤ 180 bpm
		> 180 bpm Increase or decrease from baseline > 20 bpm
6 to < 12 years	Males and Females	<60 bpm
		≥60 bpm to ≤120bpm
		> 120 bpm to ≤ 150 bpm
		> 150 bpm Increase or decrease from baseline > 20 bpm
12 to 18 years	Males and Females	< 50 bpm
		≥50 bpm to ≤100bpm
		> 100 bpm to ≤ 150 bpm

Statistical Analysis Plan

Status: Final Version 1.0

Revised: 09Jun2020

Protocol #: ZX008-1501, ZX008-1502; "Study 2"

Page 11 of 23

		> 150 bpm Increase or decrease from baseline > 20 bpm
--	--	-------------------------------------------------------------

- Overall characterization of normal and abnormal ECGs and the number and percentage of subjects with normal and abnormal ECGs. ECGs will be characterized as Normal, Abnormal Clinically Insignificant (ACI), or Abnormal Potentially Clinically Significant (APCS). The number and percentage of ECGs within each category will be calculated by dose.
- Number and percentage of subjects that develop abnormalities of repolarization on treatment, as manifest by new ST and T wave abnormalities. The number and percentage of ECGs within each category will be calculated by dose.

Analysis for specific arrhythmias: Torsade de Pointes (TdP), ventricular tachycardia/fibrillation, atrial fibrillation/flutter, supraventricular tachycardia, etc., including associations between specific ECG findings and selected clinical adverse events of interest will be explored as appropriate (events that may signal pro-arrhythmia: syncope, palpitations, dizziness, tachycardia, etc.). Shift tables will be constructed for arrhythmias.

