### 2.3.1.2 Secondary Endpoints

The secondary endpoints that will be presented by dose and subgroups are:

- QRS duration
- PR interval measurements
- Heart rate
- Categorical analyses for each variable and subgroup listed below:
  - QTcF (number and percentage of subjects, by dose)

Age	Gender	Values
0 to < 12 years	Males and Females	< 320 ms
		$\geq 320$ ms to $\leq 450$ ms
		> 450 ms to $\leq 480$ ms
		> 480 ms
12 to 18 years	Males and Females	< 320 ms
		$\geq 320$ ms to $\leq 450$ ms
	Males	> 450 ms to 500 ms
	Females	$\geq 320$ ms to $\leq 470$ ms
	Females	> 470 to ms $\leq 500$ ms
	Males and Females	> 500 ms

- F
  - or all ages QTcF changes from baseline (number and percentage of subjects, by dose)
    - $\leq 30$  ms
    - > 30 ms to  $\leq 60$  ms
    - > 60 ms

- o QRS (number and percentage of subjects, by dose)

Age	Gender	Values
2 to < 6 years	Males and Females	$\leq 90$ ms > 90 ms to $\leq 100$ ms > 100 ms
6 to < 12 years	Males and Females	$\leq 100$ ms > 100 ms to $\leq 110$ ms > 110 ms
12 to 17 years	Males and Females	$\leq 110$ ms > 110 ms to $\leq 120$ ms > 120 ms
18 years	Males and Females	$\leq 120$ ms > 120 ms

- PR (number and percentage of subjects, by dose)

Age	Gender	Values
2 to < 6 years	Males and Females	≤ 90 ms > 90 ms to ≤ 150 ms > 150 ms
6 to < 12 years	Males and Females	≤ 100 ms > 100 ms to ≤ 170 ms > 170 ms
12 to 17 years	Males and Females	≤ 110 ms > 110 ms to ≤ 180 ms > 180 ms
18 years	Males and Females	≤ 120 ms > 120 ms to ≤ 220ms > 220 ms

- o Heart rate (number and percentage of subjects, by dose)

Age	Gender	Values
2 to < 6 years	Males and Females	< 80 bpm
		$\geq 80$ bpm to $\leq 140$ bpm
		> 140 bpm to $\leq 180$ bpm
		> 180 bpm
		Increase or decrease from baseline > 10 bpm
6 to < 12 years	Males and Females	Increase or decrease from baseline > 20 bpm
		< 60 bpm
		$\geq 60$ bpm to $\leq 120$ bpm
		> 120 bpm to $\leq 150$ bpm
		> 150 bpm
12 to 18 years	Males and Females	Increase or decrease from baseline > 10 bpm
		< 50 bpm
		$\geq 50$ bpm to $\leq 100$ bpm
		> 100 bpm to $\leq 150$ bpm
		> 150 bpm
		Increase or decrease from baseline > 10 bpm
		Increase or decrease from baseline > 20 bpm

- o Overall characterization of normal and abnormal ECGs and the number and percentage of subjects with normal and abnormal ECGs. ECGs will be characterized as Normal, Abnormal Clinically Insignificant (ACI), or

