**Statistical Analysis Plan**

Sponsor: Zogenix International Limited; Protocol No.: ZX008 Study 2 (ZX008-1501 and ZX008-1502)

previous medical condition that has not worsened.

 
• Persistent cough – longer than 4 weeks without a confirmed identified pathogen (or any other persistent cough that the investigator feels is suspicious).
 

 
• Increase in blood pressure >30% from Screening blood pressure or a systolic pressure <math>\geq 140</math> mmHg after repeated measures during one visit. Blood pressure should be repeated at appropriate times within the visit.
 

 
• Jugular venous distention- visible bulging of the external jugular veins on either side of the neck
 

 
• New onset heart murmur
 

 
• Pulmonary rales – an abnormal respiratory sound heard during auscultation of the lungs, which is also described as a crackle.
 

 
• Tachycardia – a persistent HR >30% above the screening value and unrelated to exercise, exertion or anxiety. Heart rate should be repeated at appropriate times within the visit.
 

 
• Signs that could indicate right ventricular failure: 
 
• Peripheral edema
 
• Ascites
 
• Syncope
 
• Decompensated right ventricular failure – symptoms include shortness of breath, frequent coughing especially when lying flat, abdominal swelling and pain, dizziness, fainting, and fatigue
 
 
 

 
• Signs on ECHO indicative of potential valvulopathy 
 
1. valve regurgitation (aortic or mitral)
 
2. <math>\geq</math> mild valve regurgitation (tricuspid or pulmonary)
 
3. Mean Mitral valve gradient <math>\geq 4</math> mmHg
 
4. Mean Aortic valve gradient <math>\geq 15</math> mmHg
 
5. Mean Tricuspid valve gradient <math>\geq 4</math> mmHg
 
6. Mean Pulmonary valve gradient <math>\geq 21</math> mmHg
 
 
 

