## 5. Tables, Figures, and Listings

Number	Title
Table 1.1.1	Means, Mean Differences from Baseline and Upper Bound of One-Sided 95% CI from ANOVA for ECG Data - QTcF, Safety Population - Males and Females, 0 to <12 Years
Table 1.1.2	Means, Mean Differences from Baseline and Upper Bound of One-Sided 95% CI from ANOVA for ECG Data - QTcF, Safety Population - Males, 12 to 18 Years
Table 1.1.3	Means, Mean Differences from Baseline and Upper Bound of One-Sided 95% CI from ANOVA for ECG Data - QTcF, Safety Population - Females, 12 to 18 Years
Table 1.1.4	Means, Mean Differences from Baseline and Upper Bound of One-Sided 95% CI from ANOVA for ECG Data - QTcF, Safety Population - Males, 0 to <12 Years
Table 1.1.5	Means, Mean Differences from Baseline and Upper Bound of One-Sided 95% CI from ANOVA for ECG Data - QTcF, Safety Population - Females, 0 to <12 Years
Table 1.2.1	Means, Mean Differences from Baseline and Upper Bound of One-Sided 95% CI from ANOVA for ECG Data - Heart Rate, Safety Population - Males and Females, 2 to < 6 Years
Table 1.2.2	Means, Mean Differences from Baseline and Upper Bound of One-Sided 95% CI from ANOVA for ECG Data - Heart Rate, Safety Population - Males and Females, 6 to < 12 Years
Table 1.2.3	Means, Mean Differences from Baseline and Upper Bound of One-Sided 95% CI from ANOVA for ECG Data - Heart Rate, Safety Population - Males and Females, 12 to 18 Years
Table 1.3.1	Means, Mean Differences from Baseline and Upper Bound of One-Sided 95% CI from ANOVA for ECG Data - QRS Duration, Safety Population - Males and Females, 2 to < 6 Years
Table 1.3.2	Means, Mean Differences from Baseline and Upper Bound of One-Sided 95% CI from ANOVA for ECG Data - QRS Duration, Safety Population - Males and Females, 6 to < 12 Years
Table 1.3.3	Means, Mean Differences from Baseline and Upper Bound of One-Sided 95% CI from ANOVA for ECG Data - QRS Duration, Safety Population - Males and Females, 12 to 17 Years
Table 1.3.4	Means, Mean Differences from Baseline and Upper Bound of One-Sided 95% CI from ANOVA for ECG Data - QRS Duration, Safety Population - Males and Females, 18 Years
Table 1.4.1	Means, Mean Differences from Baseline and Upper Bound of One-Sided 95% CI from ANOVA for ECG Data - PR-Interval, Safety Population - Males and Females, 2 to < 6 Years
Table 1.4.2	Means, Mean Differences from Baseline and Upper Bound of One-Sided 95% CI from ANOVA for ECG Data - PR-Interval, Safety Population - Males and Females, 6 to < 12 Years

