Table 1.4.3	Means, Mean Differences from Baseline and Upper Bound of One-Sided 95% CI from ANOVA for ECG Data - PR-Interval, Safety Population - Males and Females, 12 to 17 Years
Table 1.4.4	Means, Mean Differences from Baseline and Upper Bound of One-Sided 95% CI from ANOVA for ECG Data - PR-Interval, Safety Population - Males and Females, 18 Years
Table 1.5	Means, Mean Differences from Baseline, and Mean Differences from Placebo and Baseline for ECG Data - QT-Interval, Safety Population
Table 2.1.1	Categorical Summary of ECG Data - QTcF, Safety Population - Males and Females, 0 to <12 Years
Table 2.1.2	Categorical Summary of ECG Data - QTcF, Safety Population - Males, 12 to 18 Years
Table 2.1.3	Categorical Summary of ECG Data - QTcF, Safety Population - Females, 12 to 18 Years
Table 2.1.4	Categorical Summary for ECG Data - QTcF Change from Baseline, Safety Population - Males and Females, 0 to <12 Years
Table 2.1.5	Categorical Summary for ECG Data - QTcF Change from Baseline, Safety Population - Males, 12 to 18 Years
Table 2.1.6	Categorical Summary for ECG Data - QTcF Change from Baseline, Safety Population - Females, 12 to 18 Years
Table 2.2.1	Categorical Summary of ECG Data - Heart Rate and Change from Baseline, Safety Population - Males and Females, 2 to <6 Years

Statistical Analysis Plan	
Status: Final Version 1.0	Revised: 09Jun2020

Number	Title
Table 2.2.2	Categorical Summary of ECG Data - Heart Rate and Change from Baseline, Safety Population - Males and Females, 6 to < 12 Years
Table 2.2.3	Categorical Summary of ECG Data - Heart Rate and Change from Baseline, Safety Population - Males and Females, 12 to 18 Years
Table 2.3.1	Categorical Summary of ECG Data - QRS Duration, Safety Population - Males and Females, 2 to < 6 Years
Table 2.3.2	Categorical Summary of ECG Data - QRS Duration, Safety Population - Males and Females, 6 to < 12 Years
Table 2.3.3	Categorical Summary of ECG Data - QRS Duration, Safety Population - Males and Females, 12 to 17 Years
Table 2.3.4	Categorical Summary of ECG Data - QRS Duration, Safety Population - Males and Females, 18 Years
Table 2.4.1	Categorical Summary of ECG Data - PR-Interval, Safety Population - Males and Females, 2 to < 6 Years
Table 2.4.2	Categorical Summary of ECG Data - PR-Interval, Safety Population - Males and Females, 6 to < 12 Years
Table 2.4.3	Categorical Summary of ECG Data - PR-Interval, Safety Population - Males and Females, 12 to 17 Years

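### The Study 2 cardiovascular SAP counts heart-rate rises and falls above 20 bpm in one category; separate rows would show direction at no cost

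*SAP*

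**What the plan says.** Section 2.3.1.2 of the Study 2 cardiovascular SAP sets up a categorical analysis headed "Heart rate (number and percentage of subjects, by dose"). Each of the three age bands (2 to under 6, 6 to under 12, 12 to 18 years) has absolute bands for low, middle and high rates, for example "> 140 bpm to ≤ 180 bpm" in the youngest group. Each then has one change category: "Increase or decrease from baseline > 20 bpm". Section 5 places this in Tables 2.2.1 to 2.2.3, titled "Categorical Summary of ECG Data - Heart Rate and Change from Baseline". No table shell is shown, and nothing in the text says that the two directions are tabulated apart. The Study 1 cardiovascular SAP used the same form of words, with a lower threshold as well: "Increase or decrease from baseline > 10 bpm".

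Other parts of the plan keep the sign of the change:

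- Section 2.3.1.2 also plans "Mean Heart rate (including changes from baseline" and from placebo and baseline).
- Tables 1.2.1 to 1.2.3 are titled "Means, Mean Differences from Baseline and Upper Bound of One-Sided 95% CI from ANOVA for ECG Data - Heart Rate".
- Figures 6.1 to 6.3 plot mean heart-rate change by visit.
- Section 2.3.1.3 and Listing 1.1 give subject-level values.
- The main Study 2 SAP (section 10.3, Table 6) defines tachycardia as an event of special interest: "a persistent HR >30% above the screening value and unrelated to exercise, exertion or anxiety".

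**The concern.** A rise and a fall of more than 20 bpm are opposite safety findings. If both go into one count, a reader of that row cannot tell which occurred. A drug that raises heart rate adds subjects at the upper end and removes some at the lower end, so the pooled difference between arms is smaller than the difference in rises. The falls seen on placebo also enlarge the background.

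The plan treats its closest comparators by direction. The QTcF change categories in the same section (up to 30, over 30 to 60, over 60 ms) mark only rises as outliers, and the tachycardia event of special interest is upward only. The pooled heart-rate row is out of step with both. What is at stake is how informative one descriptive table is.

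**Working it through.** **There is no plan figure to reproduce.** Section 2.4.3 says that no formal sample size calculation was made for cardiac safety, and no error rate or power is attached to this category.

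**Inputs.** The threshold of 20 bpm is from section 2.3.1.2. The SD of heart-rate change (12, 15, 18 bpm) and the mean shift (0 on placebo, +8 bpm on active) are assumptions, because the documents give neither. Heart-rate change is taken as normal, with the same SD in both arms.

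**Formulas**, with mean m and SD s:

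- rise: 1 − Φ((20 − m)/s)
- fall: Φ((−20 − m)/s)
- pooled row: rise + fall

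**Worked case, s = 15.**

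- Placebo: rise = 1 − Φ(20/15) = 9.1%, fall = 9.1%, pooled = 18.2%.
- Active: rise = 1 − Φ(12/15) = 21.2%, fall = Φ(−28/15) = 3.1%, pooled = 24.3%.
- Ratios: pooled 24.3/18.2 = 1.3; rises only 21.2/9.1 = 2.3.

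**Across the assumed range:**

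| SD (bpm) | Pooled, placebo vs active | Ratio | Rises only, placebo vs active | Ratio |
|---|---|---|---|---|
| 12 | 9.6% vs 16.8% | 1.8 | 4.8% vs 15.9% | 3.3 |
| 15 | 18.2% vs 24.3% | 1.3 | 9.1% vs 21.2% | 2.3 |
| 18 | 26.7% vs 31.2% | 1.2 | 13.3% vs 25.2% | 1.9 |

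**Could the absolute bands stand in for the row?** The middle bands run from 80 to 140, 60 to 120 and 50 to 100 bpm, so they are 60, 60 and 50 bpm wide. A child under 6 who goes from 90 to 135 bpm (+45), or an adolescent who goes from 55 to 95 bpm (+40), stays in the middle band throughout. Such a subject appears in the categorical table only through the pooled change row, without a sign.

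**The case against.** The strongest reply is that the plan already carries direction in better places. The signed mean change is planned with and without placebo correction, and it is the more sensitive comparison. With an assumed +10 bpm shift, SD of 12 to 20 bpm and 40 subjects per arm, power at two-sided 0.05 is about 61% to 96% for the mean, 35% to 55% for a rises-only row and 8% to 29% for the pooled row. High and low absolute rates are counted separately. The tachycardia event of special interest is a subject-level, upward-only measure summarised by treatment group. No test or decision rests on the row. The sponsor may also intend separate rows, since the table shells are not shown.

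Most of this stands, and it rules out three stronger readings that a reader might infer:

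- **That the direction of the cardiac signal is lost, or that all heart-rate outliers fall in one category.** The signed means, separate bands, plots, listings and event definition contradict this.
- **That this is the only subject-level comparison of heart-rate change.** The tachycardia event is another. The row is only the sole categorical count by size of change.
- **That the pooled row could stay flat or fall while rises increase.** With placebo centred at zero and equal SDs, the pooled percentage always increases with the shift. A flat row needs, for example, means of −4 and +4 bpm at SD 15 (19.8% in both arms). Nothing in the documents supports a downward drift on placebo.

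The reply does not make the row redundant. A mean does not count individual outliers. The listed heart-rate mean tables are split by age band, so the power at 40 per arm flatters them. The tachycardia event requires persistence, and listings do not compare arms.

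**Conclusion.** The point holds for this row only. As written, the sole categorical count by size of heart-rate change pools rises with falls, hides direction and weakens a one-directional contrast. The illustrated loss takes the active-to-placebo ratio from 3.3–1.9 (rises alone) to 1.8–1.2 (pooled). It depends entirely on the assumed SD of 12 to 18 bpm, the +8 bpm shift and normality. The direction of the loss does not depend on the exact values chosen within that model. No inference or conclusion of the trial turns on it. It is a minor point and a free improvement.

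**What to change.** In section 2.3.1.2 and Tables 2.2.1 to 2.2.3, replace the pooled category with two rows per age band: increase from baseline above 20 bpm, and decrease from baseline above 20 bpm. If separate rows were always intended, one sentence saying so is enough. The cost is one extra row per table, with no new data and no change to any test. No rework of Study 1 follows from this: it has already been reported, and section 4.2 excludes its 119 subjects from the Study 2 cardiovascular analysis.
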